provided. The BioFlo Port with PASV Valve Technology also claims to provide fewer complications when compared with nonvalved ports, namely a 47% ($p=0.02$) reduction in inadequate blood draw, a 51% ($p<0.03$) reduction in nursing time for troubleshooting port problems, and a 35% ($p=0.20$) reduction in tPA usage (Carlo, Lamont, McCarty, Livingston, & Kuhn, 2004). In the study by Carlo et al., the valved ports were flushed with 10 mL of normal saline while the nonvalved ports were flushed with 10 mL of heparinized saline (number of units of heparin per mL of saline not specified). These results are promising but it only included 73 patients (37 in valved port group and 36 in the non-valved port group) who were followed for 180 days. Additionally, it is only one study; subsequent studies replicating this methodology have not been located. The purpose of the MicroCLAVE® Clear connector which is used with all implanted port catheters at TriHealth is to also help minimize blood reflux into the tip of the catheter upon connection and disconnection of the luerloc, thus reducing the risk of occlusions due to blood reflux. Therefore, in this study and the one already in progress, the type of flushing solution is the main focus as the materials and mechanics of the implanted port in each study are the same.

In conclusion, Level 1 evidence for the use heparin flushes versus saline flushes for the maintenance of implanted port catheters is lacking in the current literature. No study has been conducted exclusively among patients with implanted port catheters of the same type. For nursing to establish an evidence-based practice guideline for flushing of implanted port catheters, more research is needed to generate the knowledge necessary to make recommendations that will change and standardize practice.

Research Plan

Study Design: Non-inferiority trial in which participants will be randomly assigned to one of two groups: the control group or the intervention group.

Setting for the Study: The TCI Infusion Centers, specifically: the TCI Good Samaritan (GS) Infusion Center at GSH; the TCI GS Infusion Center Butler County; the Ambulatory Treatment Center at Bethesda North Hospital; the TCI GS Infusion Center, Cheviot; TCI Infusion Center, Kenwood; TCI Infusion Center, Arrow Springs; and the TCI GS Infusion Center, Anderson.

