Participants: Patients receiving care in the identified settings who have an implanted port catheter will be recruited to participate in this study.

Inclusion Criteria:

- over the age of 18 years
- able to read and understand English
- has a BioFlo implanted port in place less than one (1) year
- evidence of a patent BioFlo port catheter prior to enrollment in the study
- is receiving active treatment i.e., receiving a therapeutic drug through the BioFlo implanted port

- current treatment protocol projected to continue for a minimum of three (3) months
- anticipates receiving care at the identified centers for 12 months following enrollment in the study
- receives routine care of the implanted port catheter at any of the identified TriHealth Cancer Institute Infusion Centers

Exclusion Criteria:

- has documented Heparin platelet antibody (could not be randomized to either group) or other allergy to Heparin
- receiving therapeutic dose of an anticoagulant, i.e., warfarin, heparin, enoxaparin, etc.
- Does not meet one or more of the inclusion criteria

Recruitment

Prospective study participants will be identified the day prior to their appointment in the treatment center by a member of the research team. Their chart will be reviewed for inclusion criteria and flagged as a potential study participant.

When the potential study participant arrives in the treatment center, a member of the research team will escort the patient into a treatment room and explain the study by reading a prepared script (see Appendix B). If the patient expresses interest, the Informed Consent Statement and HIPAA Authorization form will be reviewed and signed. After obtaining informed consent, a participant will be randomly assigned to the heparinized saline flush (control group) or saline only flush study group (intervention group). A color coded sticker will be placed on the patient's treatment folder indicating participation in the study and group assignment. The random assignment process will be achieved using sequentially-numbered opaque sealed envelopes (SNOSE) containing the group assignment. An yellow colored data collection face sheet (see Appendix C) will indicate control group; a blue colored data collection face sheet will indicate the intervention group.

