During FY 2012, 391 patients with implanted port catheters were treated in the OPCC. Seventy of these patients experienced an occlusion of their port that required the administration of alteplase (CathFlo) ([name], personal communication, October 12, 2012). Thus, 70 of 391 experienced an occlusion resulting in an occlusion rate of 18%. Some of these 70 patients experienced an occlusion more than once during that time. Additionally, during that time, a few patients had their implanted port catheters removed due to infection or malfunction. The exact number of patients who experienced multiple occlusions or had their implanted ports removed/replaced during FY2012 is unknown.

During the planning of the current study evaluating implanted port catheters, we engaged the consultation of a biostatistician through the Center for Clinical and Translational Science and Training (CCTST) to conduct a power analysis to

establish the number of participants needed in each group to determine the non-inferiority of the alternative therapy (saline only flush). Consultation was provided by [name], Associate [name] Hospital Medical Center, University of Cincinnati.

Based on the literature and our own experience we estimated an approximate occlusion rate of 20% with the standard treatment (saline + heparinized saline flush as described above). The power analysis conducted by [name] determined that, using a two group normal approximation test of proportions with a one-sided .05 significance level, a sample size of 198 participants per group will have 80% power to reject the null hypothesis that the proposed method is not inferior (i.e. the difference in proportions between the proposed method and the standard method is greater than 0.10). Thus, we will continue to recruit participants in that study until 198 have been enrolled in each group for a total of 396 study participants.

[name] was consulted again when the introduction of the BioFlo Port at TriHealth was discovered. It is [name] recommendation that this second randomized controlled trial using the same methodology and power analysis calculations be conducted. Thus, we will recruit 198 participants per group for a total of 396 participants in this study.

Data Collection:

Independent Variables: Method for flushing implanted port catheters:

- 20 mL of saline followed by 5 mL of Heparinized saline in a concentration of 100 units/mL
OR
- 20 mL of saline only

Dependent Variables:

Primary Outcomes

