The data collection tool (see Implanted Port Catheter Flushing Data Collection Form – Face Sheet: Appendix C and Record of Flushes: Appendix D) were developed by the principal and sub-investigators specifically for the purpose of this study. The tool was reviewed by the OPCC nurses for completeness and clarity. In addition to basic demographic information (age, gender), the nurse will record the patient's type of cancer, and the diagnosis or history of any hypercoaguable state or use of anticoagulant medication as documented in the patient chart. The nurse will also document the type of implanted port catheter (single/double), the port location (right/left, subclavian vein (described in the operative note or chest x-ray), and the date the port was inserted so that length of time the port has been in place can be calculated. Data will be recorded on the Face Sheet when the patient is enrolled in the study and as pertinent information/events become known, i.e., as complications occur.

With each visit to the identified treatment center, the nurse will document the date and characteristics related to the patency of the port catheter on

the Record of Flushes data collection tool. In the event the blood withdrawal is sluggish or absent, the patient will receive a dose of alteplase (CathFlo) according to the TriHealth Nursing Policy: VAD: Care & Maintenance (Appendix A) and as ordered by the physician. Dosage and results of that intervention will also be recorded on the Record of Flushes data collection tool. In the event that any study participant (regardless of group assignment) requires alteplase (CathFlo) on three (3) consecutive visits to the treatment center, the patient's participation in the study will be terminated and they will be excluded from further data collection. The patient will be returned to a standard maintenance protocol for flushing of the port as prescribed by the afore-mentioned TriHealth Nursing policy (see Appendix A) or as prescribed by attending physician.

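### The protocol does not say whether the envelope series is stratified by its seven centers, and center is neither a listed variable nor in the planned comparison; the cost is a small loss of precision

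*Combined protocol and SAP*

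**What the plan says.** The list of sites in the protocol, section Setting for the Study, opens "Setting for the Study: The TCI Infusion Centers, specifically: the TCI Good Samaritan (GS) Infusion Center at GSH; the TCI GS Infusion Center Butler County" and goes on to name five more, seven in all. Under Inclusion Criteria, a participant is someone who "receives routine care of the implanted port catheter at any of the identified TriHealth Cancer Institute Infusion Centers", so a participant is not tied to one center.

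Allocation is described under Recruitment: "The random assignment process will be achieved using sequentially-numbered opaque sealed envelopes (SNOSE) containing the group assignment". Assignment follows consent in the treatment center. The text does not give the number of series, the method of generating the sequence, any blocks or strata, or who holds the envelopes.

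Outcomes are recorded by the treating nurses: "With each visit to the identified treatment center, the nurse will document the date and characteristics related to the patency of the port catheter" (Data collection tool). The moderating variables are flushing frequency, prophylactic anticoagulant use, hypercoagulable state, mechanical difficulties and time since port placement. The extraneous variables are cancer type and age. Center is in neither list, nor among the Face Sheet items described in the text. Statistical Analysis plans a t-test, Chi-Square or Fisher's exact test between groups, a regression on the moderating variables, and stratification by flushing frequency only.

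**The concern.** In a multicenter trial one expects to read how the allocation handles center and whether the analysis does. Here center could plausibly matter. Flushing is a manual technique, and local nurses judge the outcome. Alteplase use, a listed primary outcome, is prompted by slow as well as missing blood return (Data collection tool), whereas partial occlusion is defined only as inability to withdraw blood (Primary Outcomes). Those two passages need reconciling in their own right, and meanwhile they leave room for local judgement.

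If centers differ in occlusion rate, a chance difference in center mix between the arms adds random error to the difference tested against the 0.10 margin. Stratifying by center would remove that part. The trial is sized at 80% power with no stated allowance for dropout, so even a small gain is worth having if it costs little.

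There is also a documentation gap. One numbered series can be opened in order across seven sites only if someone holds it centrally, and no such arrangement is described. Staff see the arm once assigned, so confidence in the allocation rests on envelope order, and a reader cannot tell from the protocol how that order is kept.

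**Working it through.** **Inputs from the documents (Recruitment).** Control rate: "we estimated an approximate occlusion rate of 20% with the standard treatment". Test: "using a two group normal approximation test of proportions with a one-sided .05 significance level". Margin 0.10, power 80%, 198 per group, 396 in total. The true difference is not stated; I take it as zero, which reproduces the plan's figure.

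**Plan's sample size.** n = (1.645 + 0.842)² × 2 × 0.20 × 0.80 / 0.10² = 197.8, so 198 per group. This matches.

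**Power without center.** SE = √(2 × 0.16 / 198) = 0.0402. Power = Φ(0.10 / 0.0402 − 1.645) = 80.0%.

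**Assumed center spread.** The documents give only one pooled historical rate (70 of 391, 18%). I assume seven equal centers with mean 20% and evenly spaced rates. For spacing s between neighboring centers, the between-center variance is s² × (7² − 1)/12 = 4s², so the SD is 2s. For 10-30%, s = 20/6 = 3.33 points and the SD is 6.67 points.

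**Effect of accounting for center.** The total variance 0.16 splits into a between-center part (SD²) and a within-center part (0.16 − SD²). The unadjusted comparison carries both; a center-stratified one carries only the second:

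Power = Φ(0.10 / √(2 × (0.16 − SD²) / 198) − 1.645)

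The SD of the chance shift from unequal center mix is 2 × SD / √396.

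| Assumed center rates | SD (points) | Share of variance | SD of chance shift (points) | SE with center | Power with center | n per group for 80% |
|---|---|---|---|---|---|---|
| 15-25% | 3.33 | 0.7% | 0.3 | 0.0401 | 80.3% | 197 |
| 10-30% | 6.67 | 2.8% | 0.7 | 0.0396 | 81.0% | 193 |
| 5-35% | 10.0 | 6.25% | 1.0 | 0.0389 | 82.2% | 186 |
| 0-40% | 13.3 | 11.1% | 1.3 | 0.0379 | 84.0% | 176 |

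The last row is an extreme, shown only to bound the effect.

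**Validity of the unadjusted test.** I simulated 6,000 trials per scenario with unequal center sizes (35, 20, 15, 10, 10, 5 and 5% of participants), for no center effect and for spreads of 10-30% and 5-35%. The unadjusted difference had a mean error of at most 0.04 points. Its type I error at the margin was 4.5% to 5.3%. The Mantel-Haenszel difference had type I error between 4.4% and 5.5%. I use the simulation for bias and type I error only: unequal center sizes shift the overall rate away from 20%, so its power figures are not comparable with the table.

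**The case against.** The strongest case against is that little is shown to be wrong, and most of it stands.

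- A reader might infer that the protocol describes one unstratified list shared by seven centers. It does not. The sentence on envelopes is equally consistent with one series per center. The defect is missing detail.
- A reader might infer that chance imbalance is error beyond what was planned for, or that it undermines the non-inferiority test. It is neither. The planning variance 0.20 × 0.80 = 0.16 already contains the between-center part, and the unadjusted test kept its type I error near 5%.
- A reader might infer that center, if left off the forms, is lost. The documents do not support that. An enrollment log links study code to medical record number so that missing data can be retrieved (Privacy Information), and the consent process is documented in the health record (Informed Consent). Enrolling center is probably recoverable. The Face Sheet and Record of Flushes are appendices not supplied, so absence of a center field on the forms cannot be claimed.
- Different calling of occlusion by center is plausible but not shown. Both occlusion types have written definitions, nurses giving port care are trained in study procedures, and flushing technique and connector are common to both arms.
- Center stratification would not cure error arising because assessors can see the arm.

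What survives is narrow: the scheme is unstated, center is absent from the listed variables and planned comparison, and including it is slightly more precise at very low cost.

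**Conclusion.** The point holds as a cheap improvement of minor priority. It is not a defect in the non-inferiority conclusion, and the sample size is not in error.

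Over assumed center ranges from 15-25% up to 5-35%, omitting center forgoes about 0.2 to 2.2 power points at 198 per group, equivalent to between 1 and 12 participants per group (198 − 197 and 198 − 186). These figures rest on a zero true difference and on seven equal centers with evenly spaced rates. They also assume that enrolling center captures the whole center effect. Since participants may be seen at other listed centers, and small centers would be merged, the real gain would be somewhat smaller. If center rates barely differ, there is essentially nothing to gain.

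**What to change.** 1. State the allocation scheme under Recruitment: how the sequence is generated, how many series there are, who holds the envelopes, and whether there are strata and blocks.
2. Use a separate numbered envelope series for each center, with larger permuted blocks of randomly varying, undisclosed size.
3. Record the enrolling center for every participant, and list it among the study variables.
4. In Statistical Analysis, estimate the primary saline-minus-heparin risk difference against the 0.10 margin stratified by enrolling center, for example by Mantel-Haenszel. Fix in advance the rule for merging centers with few participants.

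The cost is one data field, seven envelope sets, and a few sentences of text. No participants or visits are added and no clinical care changes. The downside is that blocking within center makes some assignments slightly easier to guess in an open-label trial; larger varying blocks limit this. If allocation has already begun, or separate series already exist, items 1, 3 and 4 can still be done; center can probably be retrieved through the enrollment log.

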Participants in the control group will have yellow colored data collection Face Sheets while participants in the intervention group will have blue colored data collection Face Sheets. The Record of Flushes sheet will be white for patients in both groups. A blue or yellow sticker will be placed on the cover of the patient folder housed in treatment center noting the patient's involvement in the study. The data collection Face Sheet and the current Record of Flushes sheet will be kept in the individual patient folder as long as they remain a participant in the study. As the Record of Flushes data sheet becomes full, they will be collected by study staff and placed in locked drawer in a TriHealth office.

Experimental Aspect of the Study:

Patients who agree to participate in this study will be randomized to either the control group or intervention group as explained above.

Participants in the control group will have their implanted port catheters flushed according to the established TriHealth Nursing Policy: Venous Access Devices (VAD): Care and Maintenance (see Appendix A). Following the use of the port catheter with no continuous fluids running, or before de-accessing a port catheter (removing the port needle), the port will be flushed with 20 ml of normal saline and 5 ml of heparinized saline in the concentration of 100 units of heparin per mL.

Participants in the intervention group will have their ports flushed with normal saline only. That is, following the use of the port catheter with no continuous fluids running, or before de-accessing a port catheter (removing the port needle), the port will be flushed with 20 ml of normal saline. Turbulent flushing technique (the solution is injected using a push/pause technique every 1 mL) will be used in both groups and all accessed port catheters will have a neutral displacement connector. The MicroCLAVE® Clear displacement connector (ICU Medical, Inc., San Clemente, CA, USA) is the current product in use. Participants in both groups will be seen in a TriHealth Cancer Institute Infusion Center at a frequency consistent with their individual treatment plan and as outlined in the TriHealth

Nursing Policy: Venous Access Devices (VAD): Care and Maintenance (see Appendix A). Participants will remain in the study for 12 months or until they experience one of the potential risks noted below. Participants will be considered as having completed the study if they participate for 12 months.

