Potential risks for study participants in either arm of the study include partial occlusion (can instill flush solution but not withdraw blood) and complete occlusion (can neither instill flush solution nor withdraw blood). Study participants could require removal of the port if an occlusion cannot be resolved, and possibly require re-insertion of a new implanted port. In the event of any occlusion, alteplase (CathFlo) in the policy established dose and frequency (see Appendix A) will be instilled to resolve the occlusion. Study participants whose implanted ports are found occluded on three (3) consecutive visits to the treatment center will be excluded from further data collection, i.e., their participation in the study will be terminated. The standard flushing as prescribed by the TriHealth Nursing Policy (see Appendix A) or as prescribed by the attending physician will be used. Study participants whose occlusion cannot be resolved with alteplase and require removal of the port will also be terminated and excluded from further data collection. Patients who develop port infections necessitating port removal will be terminated and excluded from further data collection. Study participants who develop HIT (heparin induced thrombocytopenia) or other heparin allergy will be terminated and excluded from further data collection. Likewise, patients who have thrombotic or embolic phenomenon requiring therapeutic anticoagulation will be terminated and excluded from further data collection.

The study will be closed if there is evidence that study participants in the intervention arm experience implanted port occlusion at a disproportionate rate. The amount of alteplase (CathFlo) used in each group will be assessed each month for monitoring purposes.

The undertaking of this research does require the participation of other personnel, facilities or departments other than those used in data collection. In the event the study participant is admitted to the hospital or requires some intervention using their implanted port catheter (e.g., CT scan with contrast), the study participant will have an information card describing his/her participation in the study and the group to which he/she has been randomized, so that the assigned flush solution is used, and integrity of the study can be maintained. The study participant will receive the card with instructions at the time of his/her enrollment in the study (see Appendix E Wallet Study Card).

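### The sample size of 198 per group has no allowance for participants who leave without an occlusion, and the plan does not say how they are analysed

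*Combined protocol and SAP*

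**What the plan says.** The power analysis, under Recruitment, uses a "two group normal approximation test of proportions" at a "one-sided .05 significance level", with a 20% occlusion rate on standard flushing and a margin of 0.10. It concludes that "a sample size of 198 participants per group will have 80% power". The target for this trial is then set at the same figure: "Thus, we will recruit 198 participants per group for a total of 396 participants in this study".

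Under Experimental Aspect of the Study, follow-up is 12 months: "Participants will be considered as having completed the study if they participate for 12 months". The same section lists events that end participation. One reads: "Patients who develop port infections necessitating port removal will be terminated and excluded from further data collection". The same applies to HIT or other heparin allergy, and to thrombotic or embolic events that need therapeutic anticoagulation. Two further exits, occlusion on three consecutive visits and an occlusion that cannot be resolved, follow the primary event.

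The Statistical Analysis section names t-tests, chi-square and Fisher's exact test for group differences. The documents give no expected loss, replacement rule, analysis set or rule for participants who leave before any occlusion.

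**The concern.** The number recruited equals the number that must be analysed, so nothing is left over for loss. Three of the exit rules can act before a first occlusion, and that participant's 12-month status is then unknown. The result depends on what the analyst does next, which the plan leaves open.

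If these participants are removed, power is below 80%, and a failure to show non-inferiority would be read against power the trial did not have. If they stay in the denominator as not occluded, both observed rates fall and the difference between them shrinks. In a non-inferiority trial that favours the new treatment, so the risk becomes a false claim that saline alone is adequate.

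**Working it through.** **Inputs from the protocol (Recruitment).** Control rate 0.20; margin 0.10; one-sided alpha 0.05 (z = 1.645); power 80% (z = 0.842); 198 per group. The saline-only rate is not stated and is taken as equal to control.

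**Reproducing the plan's figure.** n = 2 × 0.20 × 0.80 × (1.645 + 0.842)² / 0.10² = 197.84, so 198 per group. At n = 198 the standard error is √(0.32/198) = 0.0402, and power = Φ(0.10/0.0402 − 1.645) = 80.0%. The stated figure is reproduced, with no loss.

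**Assumption.** The documents give no loss rate d, so 5%, 10% and 20% are illustrative.

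**Case A: early exits deleted.** The number analysed per group is 198(1 − d), and power = Φ(0.10/√(0.32/n) − 1.645).

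| Loss | n per group | Power |
|---|---|---|
| 5% | 188.1 | 78.2% |
| 10% | 178.2 | 76.3% |
| 20% | 158.4 | 71.9% |

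**Case B: early exits kept as not occluded.** Assume constant hazards over 12 months, with λ = −ln(1 − p) for occlusion and μ = −ln(1 − d) for exit. The observed proportion occluded is λ/(λ + μ) × (1 − e^−(λ+μ)). At d = 20%:

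- a true 20% is observed as 18.0%;
- a true 30% is observed as 27.1%;
- a true difference of 10 points, which is the margin, appears as 9.1 points.

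With true rates of 20% and 30%, the standard error is √((0.180 × 0.820 + 0.2707 × 0.7293)/198) = 0.0417. The chance of wrongly declaring non-inferiority is Φ((0.10 − 0.0907)/0.0417 − 1.645) = about 7.8%, against the nominal 5%. With true rates equal at 20%, nominal power rises to 82.8%, so the power figure gives no warning of the problem.

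**Case C: Kaplan-Meier risk difference at 12 months, exits censored.** Under the same hazards and non-informative censoring, the large-sample variance per group is (1 − p)² × λ/(λ + μ) × (e^(λ+μ) − 1)/n, with n = 198. The numerator is 0.1643, 0.1691 and 0.1800 at 5%, 10% and 20% loss, against 0.16 with none. At 20% the standard error is √(2 × 0.18/198) = 0.0426, and power = Φ(0.10/0.0426 − 1.645) = 75.8%. At 5% and 10% it is 79.1% and 78.1%.

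**The one loss rate in the documents.** The Background gives HIT in 1–5% of patients exposed to heparin, which is 2 to 10 of 198 controls. With 196 or 188 controls against 198, power is 79.9% or 79.1%. This treats every case as preceding an occlusion and being deleted.

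**The case against.** The strongest reply is that nothing stated is miscalculated: 198 per group does give 80% power. That stands. The defect is an omission, not an arithmetic error. It is also true that participants are excluded only from further data collection, so deletion is one reading and the falls in Case A are conditional on it. The other reading, however, leads to the bias in Case B.

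The 20% is a rounded estimate with no stated time horizon, based partly on a crude one-year count of 70 of 391 (17.9%). At 17.9%, power is 82.9% with no loss and still 80.1% at 8% loss under deletion. So the lack of slack is exact only at the plan's own 20%. The HIT figure taken alone costs less than one percentage point.

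A reader might infer that heavy loss is certain, because eligibility asks only for "current treatment protocol projected to continue for a minimum of three (3) months". The documents do not support this. The next criterion requires that the patient expects care at the centers for 12 months, and the Background says that idle ports are still flushed at least every three months. The end of a drug course therefore does not end observation. A reader might also count the occlusion-driven exits as losses, but those participants have already had the first-occlusion outcome.

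**Conclusion.** The point holds as an omission. The stated 80% applies only with complete outcomes at a 20% rate. Some loss before occlusion is very likely: the protocol has three exit rules of this kind, cites HIT in 1–5%, and reports that a few ports were removed for infection or malfunction in FY2012. The size of the loss is unknown.

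If the loss is a few percent, the effect is about two points of power or less. At 20% it is either eight points of power (deletion) or a one-sided error of about 7.8% (counted as not occluded). The second is the more serious, because it favours the conclusion the trial hopes to reach. Both sets of figures rest on the assumed loss rates, and Case B also on constant hazards.

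**What to change.** 1. **Power statement (Recruitment).** Say that 198 randomised per group gives 80% power only with complete outcomes. Give the expected loss, with its basis, and the power at that loss for the analysis actually used. For the analysis in item 2 that is about 79.1%, 78.1% or 75.8% at 5%, 10% or 20%. The deletion figures in Case A should not be quoted for it.

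2. **Statistical Analysis.** Make the primary non-inferiority comparison the difference in 12-month Kaplan-Meier risk of first partial or complete occlusion, in all randomised participants, censoring those who exit without an occlusion. Time from entry to first occlusion is already a listed outcome and visit dates are already recorded, so no new data are needed.

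3. **Sensitivity analysis.** Censoring assumes that exits are unrelated to occlusion risk. This is doubtful for thrombotic events, and HIT exits may fall unevenly between the groups. Specify an analysis that varies the assumed occlusion risk after exit, by group.

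**Cost.** The stated power is slightly less favourable and rests on an added assumption. The primary analysis method also changes, so this is more than a wording change. No extra participants are needed.
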